## **10.0 Data Management**

Confidentiality protection: The data from test results will be de-identified once it has been collected and before it is stored. This means individual results would not be able to be linked to the participant by others who review the results of this research. The linkage between participant codes and identities as well as all other identifiable information including consent forms will be stored in a locked room and be accessible only to the study personnel.

Analysis: Repeated measures ANOVA with post hoc comparisons will be used to determine if each clinical hand function score improves more for the experimental compared with the control group. A significant interaction between time (pre/post) and group (experimental/control) will support the hypothesis that improvement of upper limb function will be greater with the low-level vibration stimulation.

Sample size determination: This is a pilot study using a convenience sample of children who will attend the summer CIMT camp program at MUSC.

Data sharing: Only de-identified coded data will be reported and/or shared with the public in publications, in ClinicalTrials.gov, or upon written request.

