#### **5.0 Number of Subjects**

Total Planned Enrollment: 20

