## **9.0 Study Design / Methods**

Study design: The study will be a double-blinded stratified randomized controlled trial. Consented children will be stratified in terms of their functional levels (based on MACS). Within each functional level, children will be randomly assigned to either the experimental or control group, in a balanced manner (half the children assigned to one group, and the other half assigned to the other group). All consented children will receive CIMT 6 hours/day, 5 consecutive days for 1 week. This duration of CIMT resulted in significant improvement in capacity and quality of affected upper limb functioning (Coker et al 2010, Ramey et al 2013, Coker-Bolt et al 2017). All consented children will wear the TheraBracelet device during CIMT. The device will provide treatment vibration to the experimental group and no vibration to the control group.

Blinding: A custom MATLAB program will perform group assignment and produce a treatment vibration or zero vibration file depending on the group assignment for each child. The produced vibration file will be uploaded to the TheraBracelet device for each child, and used throughout CIMT. The treatment vibration is imperceptible to healthy adults. Therefore, all personnel involved in CIMT will be blinded to the group assignment. It is anticipated that children who receive treatment vibration would not perceive the vibration from the TheraBracelet device. In an unanticipated case where a child indicates that s/he perceives vibration any time during CIMT, the vibration intensity will be lowered immediately.

Pediatric CIMT protocol: 1) The soft mitt will be worn on the child's stronger, less affected upper extremity during CIMT. 2) The child will be engaged fun, playful camp-based activities to encourage repetitive practice with the weaker limb and shaping of more mature motor responses while the mitt is being worn. These play activities will be implemented by MUSC occupational and physical therapy students who are supervised by licensed therapists. 3) Tasks such as reaching, grasping, and manipulation of objects, weight-bearing, and making hand gestures with the weaker limb will be encouraged during play activities. 4) When the children demonstrate new motor movements, students and therapists will shape and guide the quality of these movements through participation in age appropriate activities.

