Outcome Measures: Experimental and control groups will be compared for post-therapy changes in the upper limb functioning. The upper limb functioning in daily living will be measured by standard pediatric therapy parent's questionnaire assessments before and after therapy. The quality and quantity of upper limb movements will be measured by the Quality of Upper Extremity Skills Test, and the Box and Block and Nine-Hole Peg Tests, respectively. Additionally, goal attainment scaling will be used to measure achievements of goals after CIMT. Lastly, we will measure the wear time of the device and the child pain level at each CIMT day.

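### The time-by-group interaction uses neither the pre score nor the MACS stratum, so with about 10 children per arm its estimate moves with chance baseline differences that a simple adjustment would largely remove

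*Combined protocol and SAP*

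**What the plan says.** Section 10.0 (Data Management, Analysis) plans: "Repeated measures ANOVA with post hoc comparisons will be used to determine if each clinical hand function score improves more for the experimental" group than for the control group. The deciding test follows: "A significant interaction between time (pre/post) and group (experimental/control) will support the hypothesis that improvement of upper limb function will be greater" with the vibration. No covariate and no stratum term is named there or elsewhere.

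Section 9.0 (Study Design / Methods) makes the functional level part of the randomisation: "Consented children will be stratified in terms of their functional levels (based on MACS"). It continues: "Within each functional level, children will be randomly assigned to either the experimental or control group, in a balanced manner".

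Section 5.0 gives "Total Planned Enrollment: 20", and section 10.0 explains the size in one sentence: "This is a pilot study using a convenience sample of children who will attend the summer CIMT camp program at MUSC". The documents state no alpha, power, effect size, SD, pre-post correlation, number of MACS levels or stratum sizes.

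**The concern.** A pre/post interaction looks as though it accounts for the baseline, but it does so only by subtraction. Subtracting the pre score is the right adjustment only if the post score rises one for one with it. If the slope is below 1, an experimental arm that happens to start better has its effect understated, and one that starts worse has it overstated. Balancing on MACS makes large differences less likely but does not rule them out with about 10 children per arm.

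The sample is whoever attends the camp, so precision cannot be bought with more children, and the effect estimate is a pilot's main product. Two variables that would steady it, the pre score and the MACS level, are already collected and are left out of the model.

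**Working it through.** The plan gives no power or precision figure to reproduce.

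**Inputs.** From the documents: N = 20 (section 5.0) and equal allocation within MACS level (section 9.0), hence n = 10 per arm. Assumed: SD 1 at pre and post, two-sided alpha 0.05, no dropout, three MACS strata of 6, 8 and 6 children, MACS explaining half of baseline variance, and pre-post correlation rho of 0.5, 0.7 or 0.9. Two structures are used:
- Model A: MACS acts on the post score only through the pre score. The slope within strata is b = rho.
- Model B: MACS is a stable trait acting equally on both scores. Then b = (rho − 0.5)/0.5.

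**1. Identity.** Let d = post − pre, with pooled variance s² and arm means differing by Δ. The interaction mean square is nΔ²/4 and the within-child error mean square is s²/2, so F = nΔ²/(2s²) = t². On a simulated data set, both came to 4.7322 (p = 0.04317, 18 df).

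**2. Shift.** Given a baseline difference D (experimental minus control), the expected change-score estimate is the true effect + (b − 1)D. Per 1 SD of D the shift is −0.50, −0.30, −0.10 (A) and −1.00, −0.60, −0.20 (B). In simulation, pre score plus MACS leaves 0.00 in both models. The pre score alone leaves 0.00 in A but −0.54, −0.33, −0.11 in B, which is why the stratum term is included.

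**3. Likely size of D.** Var(D) = (2/10) × 0.5 = 0.10, so its SD is 0.316 and |D| is at least 0.5 SD in about 11% of trials. If MACS explained none of the baseline variance, the SD would be √0.2 = 0.45 and the chance 26%.

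**4. Precision.** Let V be the variance of the arm difference in what pre score and stratum leave unexplained: V = 0.2(1 − rho²) in A and 0.1(1 − b²) in B. The change-score variance is (b − 1)² × 0.10 + V. The adjusted variance is V(1 + 1/14), with 15 residual df.

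| Model, rho | b | V | Change score | Adjusted | Ratio | Simulated ratio |
|---|---|---|---|---|---|---|
| A, 0.5 | 0.5 | 0.150 | 0.175 | 0.161 | 0.918 | 0.915 |
| A, 0.7 | 0.7 | 0.102 | 0.111 | 0.109 | 0.985 | 0.985 |
| A, 0.9 | 0.9 | 0.038 | 0.039 | 0.041 | 1.044 | 1.043 |
| B, 0.5 | 0.0 | 0.100 | 0.200 | 0.107 | 0.536 | 0.539 |
| B, 0.7 | 0.4 | 0.084 | 0.120 | 0.090 | 0.750 | 0.751 |
| B, 0.9 | 0.8 | 0.036 | 0.040 | 0.039 | 0.964 | 0.963 |

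With b = 1 the ratio is 1 + 1/14 = 1.07, a loss. With post SD 1.2 times pre SD, simulated ratios at rho 0.7, 0.8, 0.9 are 1.05, 1.07, 1.06 (A) and 0.88, 0.99, 1.07 (B).

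**5. Simulated power and type I error (60,000 runs per setting).** Power is shown as change score to pre score plus MACS.

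| True effect | Model | rho 0.5 | rho 0.7 | rho 0.9 |
|---|---|---|---|---|
| 1 SD | A | 0.56 to 0.65 | 0.79 to 0.81 | both above 0.99 |
| 1 SD | B | 0.56 to 0.82 | 0.78 to 0.88 | both above 0.99 |
| 0.5 SD | A | 0.17 to 0.22 | 0.27 to 0.30 | 0.66 to 0.64 |
| 0.5 SD | B | 0.19 to 0.30 | 0.28 to 0.35 | 0.66 to 0.67 |

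Type I error of the planned test is 0.037, 0.042, 0.048 (A) and 0.050 to 0.051 (B). It is conservative only where MACS predicts the change. The adjusted test holds 0.050 to 0.052. Mean error over all randomisations is within 0.003 of zero for every estimator.

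**6. Both directions of imbalance.** D of 0.4 to 0.6 SD occurs in about 7% of trials each way. For a true effect of 1 SD at rho 0.7:
- Model A: the change-score estimate averages 0.85 (power 0.66, adjusted 0.78) if the experimental arm starts better, and 1.14 (power 0.89, adjusted 0.78) if it starts worse.
- Model B: 0.71 (power 0.49, adjusted 0.84) or 1.30 (power 0.97, adjusted 0.85).

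**The case against.** The planned test is valid, and it answers the question in section 9.0, which compares the arms on change. Preferring an adjusted model is a design choice. The gain depends on quantities the documents do not give, and the variance ratio runs from 0.54 to 1.07 across plausible guesses. Stratification already limits the imbalance. One SD of D shifts the estimate at rho 0.7 by 0.3 × 0.316 = 0.09 against a standard error of 0.33 (A), or 0.6 × 0.316 = 0.19 against 0.35 (B). For a 0.5 SD effect at rho 0.7, power gains at most 7 points.

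Most of this stands, and it limits the weight of the point:
- The Model B figures at rho 0.5 are an extreme bound. There b = 0, so within a stratum the pre score says nothing about the post score, which is hard to credit over a five-day programme. The gain does not depend on that case: at rho 0.6 (b = 0.2) the ratio is 1.071 × 0.096/(0.064 + 0.096) = 0.64, and at rho 0.8 (b = 0.6) it is 1.071 × 0.064/(0.016 + 0.064) = 0.86.
- Under Model A the MACS term only costs precision. The pre score alone gives ratios of 0.88, 0.95, 1.00.

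The argument that the protocol wants change does not count against adjustment. With the pre score in the model, the group coefficient is the same whether the response is the post score or the change.

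**Conclusion.** The point holds as an improvement to consider. The planned interaction is an unadjusted change-score t test: valid and unbiased on average, but sensitive to chance baseline differences unless the slope is 1. Adjusting for pre score and MACS stratum removes that sensitivity, given a roughly linear slope common to both arms. The precision gain is useful at correlations up to about 0.7, smaller at 0.8, and nil or slightly negative at 0.9 with equal SDs under Model A. The largest loss found is about 7% of variance. All sizes rest on the assumed strata, MACS share and correlations, and on 10 children per arm. A convenience sample may yield fewer.

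**What to change.** In section 10.0, replace the interaction test with wording such as: *For each clinical hand function score measured before and after CIMT, the post-CIMT score will be modelled on group, pre-CIMT score and MACS stratum, and the adjusted group difference reported with its 95% CI. A MACS level with a single child will be merged with its neighbour before unblinding. Within-group pre/post comparisons are descriptive.*

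This scope leaves out the safety items that section 12.0 also assesses before and after CIMT. Goal attainment scaling needs its own line, because section 9.0 describes it only as a measure after therapy: "Additionally, goal attainment scaling will be used to measure achievements of goals after CIMT".

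The cost is analysis wording and, with three MACS levels, a fall from 18 to 15 residual degrees of freedom. When the experimental arm happens to start worse and the slope is below 1, the adjusted test has less power than the planned one, because the planned estimate is then inflated. The review of the statistical analysis plan by the monitoring board before enrollment (section 11.0) is a natural point to make the change, so that the covariates are fixed before results are seen.

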## **11.0 Provisions to Monitor the Data to Ensure the Safety of Subjects**

Data and Safety Monitoring Board (DSMB): The primary purpose of the DSMB is to ensure the safety of participants and the validity and integrity of data collected during the study. By having the DSMB, safety concerns will be assessed and addressed objectively. If the intervention definitively has safety concerns, the DSMB may make recommendations to address the safety concerns.

The DSMB will be composed of (1) a board certified physician with expertise in neurologic disorders, (2) a registered and licensed occupational therapist with expertise in rehabilitation, and (3) a biostatistician with expertise in design and analysis of clinical trials.

The responsibilities of the DSMB are as follows. Prior to enrollment, the DSMB will review the study design, protocol, recruitment/enrollment plan, statistical analysis plan, and data safety monitoring plan, and document the agreement or recommendation. After enrollment begins and the CIMT camp is provided, the DSMB will convene again to review the safety data, enrollment data including any discontinuation of participation in the study with or without adverse events, and study results. Safety data will include emergence of skin irritation, increase in muscle tone, reduction in the number of functional tasks completed by children, worsening in the quality of motor movements in children, and any other adverse events noted by camp counselors and/or licensed therapists, regardless of whether it is related to the device use or not. The DSMB will review the aggregated summary data as well as the individual participants' data (de-identified). The DSMB will have access to coded (de-identified) data but not identifiable data. The group

assignment information will become available upon completion of the data collection. The DSMB will provide recommendations for adverse events and safety concerns. The DSMB will also provide a report to the IRB to summarize oversight activities, recommendations, and any concerns regarding participant safety.

Reporting: All safety data including adverse events will be reported to the DSMB and IRB. Summative data will be reported in ClinicalTrials.gov and in publications. Following the guidelines, we will register this study in ClinicalTrials.gov as soon as the study commences (at the latest within 21 days after the first participant is enrolled) and report results including all adverse events as soon as the study is completed (at the latest within 12 months of the trial's primary completion date). To protect participants' confidentiality, personally identifiable information will not be used for reporting. Only de-identified or aggregated data will be used for reporting.

Endpoint: Participants will be assured of their right to discontinue their participation in the study at any time. In addition, [name] may recommend discontinuation of participation if his/her adverse event is deemed to warrant discontinuation, without breaking the double-blinding.

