## 2.0 Background

Pediatric CIMT is one of the most effective treatment approaches for children with unilateral motor weakness or hemiparesis, regardless of the neuromotor impairment's etiology (Ramey et al. 2013). CIMT involves applying a hand splint and mitt on the stronger, unaffected upper extremity a hand splint and mitt on the stronger upper extremity to encourage use of the affected upper limb in intensive therapy. Research evidence supports the use of intensive therapy models, such as CIMT, to improve overall function in adults and children with one-sided motor weakness or a hemiparesis (Taub et al. 2007 & 2004, Eliasson et al. 2005, Brady and Garcia 2009, Case-Smith et al. 2012, Huang et al. 2009, Coker et al. 2009, DeLuca et al. 2003, 2007, 2012a,b, Nelles 2004, Sakzewski et al. 2009, Al-Oraibi and Eliasson 2011, Barry 2001, Bower and McClellan 2004).

[name], OTR, FAOTA co-developed and currently hold a yearly one-week modified pediatric CIMT camp at MUSC which has provided an intensive CIMT therapy program for over 200 children (approximately 3 to 9 years of age) with hemiplegic CP since 2001 and is an ongoing annual effort. The camp provides a hands-on learning opportunity for occupational and physical therapy students who serve as camp counselors under the mentorship of licensed therapists. The intensive group-based day camp program is now embedded into the occupational and physical therapy course curriculum and a systematic course with training modules has been developed to teach students how to provide the essential components of pediatric CIMT. The children that have participated in this intensive 30 hour CIMT program have demonstrated significant improvements in overall self-care, upper extremity function and mobility skills (Coker et al 2010, Ramey et al 2013).

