vibration daily (e.g. from a phone, riding a car). Truck drivers who get exposed to whole-body vibration are limited to driving 11 hours after 10 consecutive hours off duty, according to Federal Motor Carrier Safety Administration. TheraBracelet has been used during 2-week therapy (2 hours/session, 3 sessions/week for 2 weeks) in adults with stroke and resulted in significantly greater improvement in the hand dexterity score compared to dose-matched therapy with no TheraBracelet, without adverse events (i.e., no skin irritation, no numbness) in the PI's previous study (in review). In the PI's current study, TheraBracelet is being used all day (during waking hours), everyday, for a month, in adult stroke survivors, without a safety concern thus far. TheraBracelet has not been used in children, although high-level (i.e. perceivable) vibration has been used in children with CP to treat spasticity and motor function (Katusic et al. 2013).

Control/placebo: No vibration will be the control condition. The MP3 player will play a zero-amplitude file, producing no vibration.

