## **12.0Risks to Subjects**

- Confidentiality: There is a risk for loss of confidentiality.
- Injury: There is a risk for injury during engagement in play activities involved in therapy interventions. Although therapy interventions used in the pediatric CIMT involve those play activities that a child would normally engage in during a typical day, children are at risk for injury during play and daily activities. There is a risk of physical and mental fatigue from engaging in the CIMT.
- Mitt restraint: There is a risk of skin breakdown or irritation from the soft mitt restraint and stiffness in the less involved limb being constrained. The children could become frustrated or anxious from having their stronger hand restrained for several hours a day.
- Randomization: The treatment a person receives may prove to be less effective or to have more side effects than the other study treatment or other available treatments.
- Watch/Vibration: There is a minor risk of skin irritation from wearing the wristband and/or from vibration. There is a minor risk of discomfort in moving the arm/hand due to the weight of the device on the wrist, although the device weighs only 40g. Potential risks that may be associated with prolonged use of wrist vibration, including irritation, muscle tones, reduction in the number of functional tasks completed by children, and worsening in the quality of motor movements in children will be noted during each day of CIMT, and formally assessed during pre/post assessments.
- There is also a risk of unexpected medical emergencies.

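### Safety data come from camp staff on camp days and at the pre/post assessments; no parent query and no end date for safety observation are described, so some events may be missed

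*Combined protocol and SAP*

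**What the plan says.** Section 11.0 (DSMB) lists the safety data: skin irritation, raised muscle tone, fewer functional tasks completed, poorer movement quality, and "any other adverse events noted by camp counselors and/or licensed therapists", whether or not related to the device. Section 12.0 (Watch/Vibration) gives the timing: the possible risks of prolonged vibration "will be noted during each day of CIMT, and formally assessed during pre/post assessments". Section 9.0 (Outcome Measures) adds a pain level on each CIMT day.

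The only parent input described is the questionnaire in section 9.0, given before and after therapy, and it concerns upper limb function in daily life. Under section 15.0 the device is handed back when the child leaves each day.

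On exposure, section 9.0 says "All consented children will receive CIMT 6 hours/day, 5 consecutive days for 1 week" and "All consented children will wear the TheraBracelet device during CIMT". Section 3.0 says that the device has not been used in children. It describes a previous adult stroke study ("2 hours/session, 3 sessions/week for 2 weeks") with no adverse events, where skin irritation and numbness are named as absent. It also describes a current adult study in which "TheraBracelet is being used all day (during waking hours), everyday, for a month, in adult stroke survivors, without a safety concern thus far".

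Section 11.0 (Reporting) undertakes to report all adverse events. Section 13.0 justifies the risks partly by what will be learned about safety.

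**The concern.** In a day camp the family has the child each evening and night, and all the time after the last session. Skin changes, altered tone, soreness or numbness could show themselves after the device comes off. The people best placed to see this are the parents, and no described procedure asks them. Numbness is part of the adult safety result in section 3.0 but is not named in the list in section 11.0. As described, it would have to be noticed by staff or volunteered by a child of 3 to 9 years.

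With about 10 children receiving vibration, the safety result will be a very small count, possibly zero. A zero reassures only as far as events were looked for. If transient home events go unasked about, the trial could report no adverse events without knowing whether there were any. The DSMB meets again only after the camp, when unrecorded home events would be hard to recover.

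**Working it through.** **Exposure.** Scheduled hours = hours per session × sessions.
- Children (section 9.0): 6 × 5 = 30 h. This reproduces the 30-hour programme stated in section 2.0.
- Previous adult study (section 3.0): 2 × 3 × 2 = 12 h. The ratio is 30/12 = 2.5 in total and 6/2 = 3 per session, with fewer sessions (5 against 6).
- Current adult study (section 3.0): hours per day are not given. Assuming 12 to 16 waking hours for 28 to 30 days gives 12 × 28 = 336 h to 16 × 30 = 480 h, which is 11 to 16 times the children's 30 h.

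**Observation window.** Assume that sessions start at the same time on five consecutive days.
- Start of day 1 to end of day 5: 4 × 24 + 6 = 102 h.
- Camp hours: 30/102 = 29%.
- Remainder: 102 − 30 = 72 h, in four gaps of 18 h. Each gap is followed by a camp day with staff present.
- After day 5: the only described look is the post-therapy assessment, with no date given.

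**What the described methods can reach.**

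| Event | Described route to the safety data |
|---|---|
| During camp hours | Staff observation; daily pain level |
| Begins at home, persists to next camp day | Staff may see it |
| Begins at home, resolves before arrival | None, unless volunteered |
| After day 5, still present at the post-test | Formal post-therapy assessment, for the listed risks |
| First appears after the post-test | None |

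**Effect of incomplete capture.** Planned enrollment is 20 (section 5.0), split in half (section 9.0), so n is about 10 on vibration. For true event rate p per child and an assumed share c of events captured, P(at least one recorded) = 1 − (1 − pc)^10:

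| p | c = 1 | c = 0.75 | c = 0.5 | c = 0.3 |
|---|---|---|---|---|
| 5% | 40% | 32% | 22% | 14% |
| 10% | 65% | 54% | 40% | 26% |
| 20% | 89% | 80% | 65% | 46% |

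For zero events in 10 children, the one-sided 95% upper limit is 1 − 0.05^(1/10) = 25.9% with full capture. With half captured, the limit applies to the recorded rate, so the true rate is bounded at 25.9%/0.5, about 52%. The documents give no value for p or c, so these figures are illustrations.

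**The case against.** The best defence is that the documents do not exclude parent reports. The phrase in section 11.0 says who notes an event, and staff could note one that a parent mentions at drop-off. Section 11.0 also has the DSMB review a data safety monitoring plan before enrollment, and the consent form, which might tell parents how to report, is not among the pages available. This stands: a reader might infer that parents are shut out, but the text is only silent. The defence does not supply an active query, however, and the sections that define the safety data describe none.

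A reader might also infer that 72 hours go unobserved and their events are lost. That is too strong. The 29% is a share of clock time, sleep included, and not a share of events missed. Persisting events can be seen next morning or at the post-test.

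A third tempting reading is that children receive 2.5 times the known adult exposure. The ratio is correct for the previous adult study only. The current adult study involves far more hours, without a concern so far. It is unfinished and in adults, so it does not settle safety in children, but the ratio should not stand alone.

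Two further limits apply. The observers include licensed therapists as well as students. Stiffness, fatigue and frustration are listed in section 12.0 under the mitt and CIMT, which both arms receive, so they do not bear on the novelty of vibration.

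**Conclusion.** The gap is real but narrow. Sections 11.0 and 12.0 describe no active parent query about events outside camp hours and no safety contact after an undated post-therapy assessment. Two kinds of event may therefore be missed: transient ones at home that nobody volunteers, and ones that first appear after the post-test. In a first use in children, this weakens the promised safety conclusion.

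How many events would be lost cannot be computed from the documents. As an illustration, at an assumed true rate of 10% and half of events captured, the chance of recording any event among 10 children falls from 65% to 40%. The 26% upper limit for 0 of 10 should not be read as evidence of under-capture: it comes from the sample size, and better collection would not lower it. Better collection would make it a fair statement of what a zero count means.

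The conclusion rests on about 10 children receiving vibration and on no parent query being set out in material outside these pages. If one exists, it needs only to be stated in section 11.0.

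**What to change.** In section 11.0, name the parent or guardian as a source of safety data. Use a short fixed checklist (skin, pain or numbness, stiffness or tone, arm use, distress) at each morning arrival and at the post-therapy assessment. On days 2 to 5 it would cover the time since the previous session. Use the same form and timing in both arms, with parent and recorder blind to group.

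Give the timing of the post-therapy assessment and state when safety observation ends. One brief later message or call by existing personnel is preferable but more optional, since the documents point to no specific delayed risk. If it is added, complete it before the group assignment is released, which section 11.0 ties to the end of data collection. Report the parent-reported events by arm to the DSMB beside the staff-noted events.

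The cost is a one-page form at contacts that already take place and, if the later contact is kept, 20 messages or calls. More minor, unrelated events will be recorded, which should fall equally on both arms and so leave the comparison between them fair. Treatment and the efficacy analysis do not change.
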